# 8. PROGRESS REPORT

Not applicable

### Study Procedures/Activities

A woman scheduled to undergo urogynecologic surgery will be informed by her surgeon she is eligible for study enrollment at her standard-of-care pre-operative appointment. At that time, if the patient wishes, written informed consent will be obtained and the patient will be assigned a study identification (ID) number. On the day of surgery, the patient will meet with her surgeon briefly again in the pre-operative area to confirmed continued design to participate in the study and to review the surgical plan. Premenopausal subjects (i.e. last menstrual period less than 1 year ago) who have not previously undergone hysterectomy undergo a urine pregnancy test as part of their standard clinical care to assure non-pregnant status on day of surgery. The results of this test will be utilized to determine final study eligibility, i.e. those who are determined to be pregnant will be excluded from the study. Regardless of study group assignment, the subject will receive pre-operative intravenous prophylactic antibiotics, which is the standard of care per hospital policy. Once the subject is in the operating room and has undergone induction of anesthesia and placement of a transurethral catheter for clinical care, a urine sample will then be obtained at the start of the case. A vaginal swab will also be obtained. The process of obtaining these samples will take less than 1 minute and will not significantly prolong anesthesia time. These samples will be saved for microbiome analysis. The planned surgery will then be performed. Then, while still under general anesthesia and during the final safety cystoscopy performed for the subject's standard clinical care, if the patient has not had any intraoperative events that exclude her from the study, the surgeon will open the patient's randomization envelop to determine study arm assignment (to gentamicin or no instillation group). After a final foley catheter is placed, for the subject's standard clinical care, another urine sample for microbiome analysis will be obtained, as will a vaginal swab for vaginal microbiome analysis. Then, if the patient is randomized to gentamicin, 80mg of gentamicin in 50 mL of normal saline will be infused into the patient's bladder through the standard-of-care transurethral catheter by the surgeon. The surgeon will then clamp the catheter and label the catheter with the clamping time. If the patient is randomized to no instillation, the surgeon will clamp the catheter and label the catheter with the clamping time. The purpose of clamping the catheter for subjects receiving usual care will be to ensure patients are blinded if they wake up and notice their catheter. The subject will then proceed

as usual to the postoperative anesthesia care unit (PACU), with instructions for the PACU nurse to unclamp the catheter 1 hour after the clamping time. All patients will then receive usual postoperative care including an active voiding trial as indicated. During the voiding trial, which is performed as part of the subject's standard clinical care, the transurethral catheter is disconnected from the collection bag. Then the subject's bladder is backfilled with approximately 300 mL of sterile water or saline. The catheter is then removed and the patient is instructed to urinate. The voided volume is measured. The post-void residual is also measured non-invasively by bladder scan.

After surgery, as is part of routine care, the patients will call the surgeon's office if they have UTI symptoms and these calls will be addressed in the usual fashion by the nursing and physician office staff. The patients will give catheterized urine samples as indicated for UTI symptoms which will be processed at a UCSD laboratory.

At 6 weeks after surgery the patient will be seen for a standard-of-care postoperative appointment. At this time, the patient will undergo some standard-of-care health questions related to post-operative healing and any adverse health events since surgery. For the specific purposes of the study and at the FDA's recommendation, all patients at the 6 week post-operative visit will be asked whether they have experienced new onset of hearing loss, tinnitus, dizziness, or vertigo since surgery. For the purposes of the study, if the patient does not come to their post-operative appointment, they will be called at to see whether they have been treated for UTI or have UTI symptoms since surgery. They will also be asked about any other adverse health events since surgery.

Visit	Timing	Purpose	Location	Time Required	Testing
1	Within 4 weeks of surgery	Standard-of-care preoperative counseling, study recruitment and informed consent process	WPMC	60 minutes	Standard-of- care complete blood count, serum electrolytes, serum creatinine and blood urine nitrogen, pregnancy test for women of childbearing potential, and urinalysis and/or urine culture for all patients
2	Day of Surgery	Surgery, Randomization, Study Intervention (gentamicin instillation versus only catheter clamping), Standard- of-care post-operative care	JMC/KOP	Approximately 8 hours (depending on surgery length)	Standard of care pre- operative pregnancy test for appropriate patients, 2 catheterized urine specimens and 2 vaginal swab specimens for microbiome analysis
3	6 weeks after surgery day	Standard-of-care postoperative assessment	WPMC	60 minutes	Standard of care urinalysis and/or urine culture if UTI symptoms

Procedures/Interventions Performed Solely For Research Purposes

The procedures/interventioned performed solely for research purposes include the collection of urine samples and vaginal swab samples immediately before and after the urogynecologic surgery, as well as the instillation of gentamicin (if randomized to that arm), and the clamping of the catheter in both study arms. Post-operative questions regarding new onset of hearing loss, tinnitus, dizziness, or vertigo since surgery are also specifically for the study due to the FDA's recommendation in the IND

approval process. Finally, the telephone call at 6 weeks if the subject does not come to their scheduled follow up appointment will be for the purpose of collecting study data. All other aspects of the study are routine clinical care that the subjects would be undergoing even if they were not participants in the study.

### IND Requirement

Gentamicin sulfate is FDA approved for treatment and prevention of bacterial infections in adults given by intramuscular or intravenous route. Our study proposes the use of gentamicin sulfate 80mg in 50 mL of normal saline administered directly into the bladder via transurethral catheter to prevent post-operative UTI infection. The subject would have this standard-of-care catheter at the end of the surgery regardless of participation in the study. Due to our proposal for a new route and indication, and Investigational New Drug application has been filed with the FDA (IND 146413) and we have been cleared to proceed with this proposed trial as of November 15, 2019. See attached documents for IND correspondence with the FDA.

# Study Procedures for Obtaining Research Material

All research material will be stored labeled with subject study ID rather than identifying characteristics. All material will be collected specifically for research purposes and will not be saved for future use after the current study is concluded. Urine samples will be collected by a transurethral catheter placed as part of the subject's standard clinical care immediately before and after the surgery while the subject is still under general anesthesia. Vaginal swabs will be collected at the same time. Other study material will be collected by manual abstraction of data from the electronic medical record. No audio or video recording will be performed as a part of the study. No questionnaires will be used for the study.

### Data Collection

An encrypted electronic database will be used to compile study data. All subjects will have a unique study ID linked to protected health information stored separately in a locked room at WPMC only accessible to study personnel. The data will be entered into the database by study ID.

Baseline subject data will be collected including patient name, medical record number, date of birth, telephone call for phone follow up, age, body mass index (BMI), parity, race, ethnicity, prior hysterectomy, history of diabetes mellitus, American Society of Anesthesiologists (ASA) Physical Status Class, menopausal status, use of hormone replacement therapy within 3 months, use of vaginal estrogen within 3 months, history of recurrent UTI, and positive pre-operative UTI.

At the end of each surgery, the surgeon will record the following information on an OR Form which will be later entered into the data base – procedures performed, procedure start and end time, number of cystoscopies, resident and/or fellow involvement and year of training, estimated blood loss, IV antibiotic received pre-operatively and whether or not it was appropriately re-dosed as indicated. These OR forms will be kept in a secured box in the Women's Pelvic Medicine Center with only co-investigators and study staff having access. The OR forms will be labeled by study ID.

The following information will be extracted from the patient's chart for the post-operative period - length of hospital stay in days, length of initial immediate post-operative catheterization (in days), results of initial active voiding trial, need for continued postoperative catheterization after hospital discharge (and if so -, type of post-operative catheterization [indwelling or intermittent] and duration [in days]), post-operative UTI treatment and urine culture result if applicable, patient reports of dizziness, tinnitus, hearing loss, or vertigo, and hospital readmission. This information will be added to the electronic database.

Results of intraoperative urinary and vaginal microbiome results will also be added to the electronic database.

Prior to final analysis, the investigators will make efforts to resolve any missing data by a final review of the electronic medical record.

Based on previously published data regarding safety of intravesical gentamicin, we will focus specifically on gathering data related to suprapubic discomfort and development of antibiotic-resistant UTI. Other adverse events during the study period, including death and hospital admission, will also be recorded. Per FDA request we will also monitor for ototoxicity including dizziness, vertigo, hearing loss, and tinnitus. Study investigators will review the study database every 6 months to analyze incidence of adverse events. If there is a 10% or greater incidence of serious adverse event among participants (i.e. unanticipated hospital admission), the research team will meet to discuss potential for serious adverse event to be related to intravesicular gentamicin, study modification, or termination.

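### The 10% serious-adverse-event trigger names no arm and, read plainly, pools treated and untreated women, so it can miss a several-fold excess on gentamicin when the control rate is low

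*Combined protocol and SAP*

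**What the plan says.** The safety monitoring text stands in section 9, at the end of Data Collection. It provides for periodic review: "Study investigators will review the study database every 6 months to analyze incidence of adverse events". It then sets one numerical trigger: "If there is a 10% or greater incidence of serious adverse event among participants (i.e. unanticipated hospital admission), the research team will meet". The consequence in full is that "the research team will meet to discuss potential for serious adverse event to be related to intravesicular gentamicin, study modification, or termination". No basis for the 10% is given.

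The same paragraph also says: "Other adverse events during the study period, including death and hospital admission, will also be recorded".

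Three other parts of section 9 bear on the point:

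- Study Procedures/Activities: control women have the catheter clamped and receive no drug.
- Data Analysis/Interpretation: recruitment is 200 per arm. Listed adverse events, including death and admission with organ dysfunction, are compared by arm with a chi-squared test. That comparison is not tied to the 6-monthly reviews.
- Overview: only the subject is blinded.

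**The concern.** The trigger's denominator does not match its purpose. The meeting is to "discuss potential for serious adverse event to be related to intravesicular gentamicin", which is a question about the treated arm. A rate taken over all participants averages that arm with an equal number of untreated women, so at 1:1 allocation an excess in the gentamicin arm enters the pooled rate at half its size. If serious events are uncommon in controls, the treated arm could have several times the control rate while the pooled figure stays below 10%.

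The event definition raises a second, smaller matter. Taken literally, the abbreviation in the parenthesis equates a serious adverse event with unanticipated admission. A death without admission would then not count towards the trigger, although the same paragraph records deaths.

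At stake is whether the one stated prompt for a safety discussion works as intended, in a trial that gives a drug by a new route and for a new indication under an IND.

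**Working it through.** **Inputs from the documents.** Trigger: 10% or more, no arm named. Arms: 200 each, so 1:1. Recruitment benchmark: about 50% at 6 months, so about 100 per arm. The 10% has no derivation, so there is no figure of the plan's own to reproduce.

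**Assumed inputs.** The documents give no admission or serious-event rates. Control rates (pC) of 0% to 5% and a range of gentamicin-arm rates (pT) are assumed. Each probability is for a single look.

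**Step 1: dilution.** With equal arms the pooled rate is (pC + pT)/2. Setting this to 10% gives pT = 20% − pC:

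- pC = 0%: pT = 20%
- pC = 2%: pT = 18%
- pC = 5%: pT = 15%

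A rise from 2% to 10%, a five-fold excess, gives a pooled rate of (2% + 10%)/2 = 6%.

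**Step 2: probability of reaching 10% with 100 per arm.** Let X be the number of events in controls and Y the number in the gentamicin arm, independent binomials.

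- Pooled reading: P(X + Y ≥ 20), with X ~ Bin(100, pC) and Y ~ Bin(100, pT).
- Gentamicin-arm reading: P(Y ≥ 10).

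| pT vs pC | Pooled | Gentamicin arm |
|---|---|---|
| 10% vs 2% | 1.6% | 55% |
| 10% vs 5% | 12% | 55% |
| 15% vs 2% | 25% | 94% |
| 15% vs 5% | 54% | 94% |
| 20% vs 5% | 89% | 99.8% |

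**Step 3: full recruitment, 200 per arm.** The limits become 40 events pooled and 20 in the gentamicin arm.

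| pT vs pC | Pooled | Gentamicin arm |
|---|---|---|
| 10% vs 2% | 0.1% | 53% |
| 15% vs 2% | 16% | 98.5% |
| 15% vs 5% | 52.5% | 98.5% |

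For 10% and 15% against 2%, where the true pooled rate is below 10%, the pooled trigger becomes less likely to trip as data accumulate.

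**Step 4: no drug effect.** With 10% in both arms and 100 per arm, the pooled trigger trips 53% of the time. Reaching it therefore says little about gentamicin unless the arms are separated.

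**Step 5: chance triggers under the gentamicin-arm reading, per look, no drug effect.**

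| True rate in both arms | Per arm | Gentamicin arm | Pooled |
|---|---|---|---|
| 5% | 100 | 3% | 0.3% |
| 5% | 50 | 10% | 3% |
| 8% | 100 | 28% | 18% |

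The smaller arm size matters. The 6-month benchmark counts women recruited, consent may precede surgery by up to 4 weeks, and follow-up runs 6 weeks after it. Fewer than 100 per arm would have complete safety data at that review.

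**The case against.** The strongest reply is that the trigger does not control access to safety review. Investigators examine adverse events every 6 months whatever the rate, and nothing stops them meeting below 10%. With only the subject blinded, they could look by arm if they chose. A reader might infer that an excess below the threshold would go unseen, and the documents do not support that. What remains is that the review is not stated to be by arm, and the by-arm comparison in Data Analysis/Interpretation is not linked to it.

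A reader might also infer that the pooled trigger would usually fail. That depends on the assumed rates: it trips 54% of the time at 15% against 5%, and 89% at 20% against 5%. Misses are the likely result only when the control rate is low or the excess is smaller. Repeated looks are not modelled.

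Pooling is the plain reading but is not spelled out; the text says neither all participants nor by arm. Holding 10% fixed while narrowing the denominator also makes the rule stricter whenever the treated arm is worse, so part of the contrast is a lower bar. The plan does not say what the 10% was meant to represent, so the choice is one of design.

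On deaths, the abbreviation may be a slip for one that introduces an example. Deaths are recorded and compared by arm at the end, and few would move a 10% rate. It would be wrong to say that the plan ignores deaths; the wording needs reconciling.

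Finally, some pages and the IND correspondence are not in the supplied text, so it cannot be said that the trial has no other safety threshold.

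**Conclusion.** The point stands as a cheap improvement. The trigger asks a question about gentamicin but, read plainly, measures a rate that half-dilutes the gentamicin signal. With assumed control rates of 0% to 5%, the gentamicin-arm rate must be 15% to 20% before the true pooled rate reaches 10%. It can therefore miss a several-fold excess when the control rate is low, and it can equally be reached with no drug effect. Only the 1:1 allocation and the 10% come from the plan; every event rate is an assumption, and the probabilities are for a single look. The finding concerns the trigger alone and does not show that safety monitoring as a whole would fail. The omission of a death without admission is a literal consequence of the wording and should be settled in the text.

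**What to change.** At each 6-monthly review, tabulate serious adverse events by arm, with the between-arm difference and its confidence interval. Read the plan's own 10% against the gentamicin arm as well as overall, and say so in the text. Reconcile the parenthetical definition with the recording of deaths, so that every serious adverse event, including death, counts. No new threshold or stopping rule is proposed.

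The cost is one table at reviews already scheduled. Because only the subject is blinded and the surgeon opens the envelope, it breaks no stated blind. The downside is more meetings prompted by chance, at the per-look rates in Step 5 of the working: 3% in the most favourable case shown and 28% in the least. The consequence of a chance trigger is a discussion.

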#### Data Analysis/Interpretation

Subjects' data will be analyzed "as treated". Preoperative and perioperative variables will be summarized by means with standard deviations for continuous variables and rates and proportions for categorical variables. To determine whether any significant baseline differences exist between the study arms, preoperative and perioperative variables of the two study arms will be compared using chi-square test for categorical variables or Student t-test or Wilcoxon rank sum test for continuous variables.

The primary outcome of the study, proportion of patients who are clinically treated for UTI, will be analyzed with a chi-squared test. All adverse events will be listed with description of type and severity. The proportion of patients with each type of postoperative adverse event (diarrhea, yeast infection, hospital admission with organ dysfunction, and death) in each arm will also be compared using a chi-squared test. Statistical significance will be defined as  $\alpha$ <0.05.

In order to perform our sample size calculation, we first wanted to baseline postoperative UTI rates according to the definition of our primary outcome at our institution. Chart queries were performed for all GIVE-IT candidates during 2-month time period (Jan-Feb 2019; N=41) at Kaiser San Diego (our FPMRS fellowship sister institution), as it is currently our practice at UCSD (but *not* at Kaiser) to prescribe oral antibiotic prophylaxis following SUI surgery, which could alter UTI rate. The UTI rate in this chart query was 17%. To detect a meaningful reduction in UTI from 17% in controls to 8% in intervention group ( $\alpha = 0.05$ , one-tailed) with 80% power ( $\beta = 0.2$ ), 166 subjects will be needed per arm. This effect of 50% reduction as a meaningful outcome is derived from the similar effect of oral antibiotic post-operative UTI prophylaxis seen in a similar clinical trial. Accounting for 20% dropout or loss to follow-up, we will recruit 200 subjects per arm. Our benchmark for successful recruitment will be approximately 50% recruitment completed 6 months after the first subject is enrolled. In order to complete enrollment more rapidly, we anticipate adding Kaiser San Diego as a secondary study site.

All of the patients in the study will be women. Based on a retrospective population-based cohort study of 149,554 American women, there was an 11.1% lifetime risk of undergoing a single surgery for prolapse or incontinence by age 80. In another population based cohort study of 2270 middle-aged and older racially diverse American women (44% white, 20% African American, 18% Asian, and 18% Latina or other), 19% of the Latina women, 7% of the Asian women, and 5% of the African American women reported bothersome prolapse. A study of the same cohort found that 36% of Hispanic women, 25% of African American women, and 19% of Asian America women reported weekly urinary incontinence. The study will not specifically recruit or exclude minority ethnic groups. Based on the clinical population at WPMC, approximately 30% of the subjects are expected to be Latina, 10% Asian, and 5% African American.

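### The by-arm adverse-event comparison omits the safety events the plan says it will focus on or monitor at FDA request, and two of them lack a consistent way of being asked about

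*Combined protocol and SAP*

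**What the plan says.** The last paragraph of Data Collection sets the safety targets. It states that "we will focus specifically on gathering data related to suprapubic discomfort and development of antibiotic-resistant UTI", and then: "Per FDA request we will also monitor for ototoxicity including dizziness, vertigo, hearing loss, and tinnitus". It adds: "Other adverse events during the study period, including death and hospital admission, will also be recorded". The same paragraph has investigators review the database every 6 months and sets a 10% threshold on the "incidence of serious adverse event among participants (i.e. unanticipated hospital admission").

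Earlier in Data Collection, the items taken from the chart include "post-operative UTI treatment and urine culture result if applicable, patient reports of dizziness, tinnitus, hearing loss, or vertigo, and hospital readmission". Suprapubic discomfort, diarrhea, yeast infection and death are not among them.

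Under Study Procedures/Activities, all women at the 6-week visit "will be asked whether they have experienced new onset of hearing loss, tinnitus, dizziness, or vertigo since surgery". These are the only symptom questions marked as added for research: "Post-operative questions regarding new onset of hearing loss, tinnitus, dizziness, or vertigo since surgery are also specifically for the study". The visit also has an open question on adverse health events. The telephone call for women who miss the visit covers UTI treatment, UTI symptoms and any other adverse health events. It does not name the ototoxicity symptoms.

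Data Analysis/Interpretation promises a listing of all adverse events by type and severity, without saying that it is by arm. It then specifies the comparison of the proportion of patients with each type of event: "diarrhea, yeast infection, hospital admission with organ dysfunction, and death) in each arm will also be compared using a chi-squared test".

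**The concern.** The events chosen as the safety focus are not the events chosen for comparison. A statistician who follows the analysis section as printed will compare diarrhea and yeast infection between arms. The same statistician will produce no by-arm estimate for suprapubic discomfort, resistant UTI or ototoxicity.

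Two kinds of loss are possible, and they differ in how far they can be repaired. Ototoxicity symptoms and culture results are extracted, so a by-arm table could still be made later, although it would then be unplanned. A symptom that was not asked about, or was asked about differently by route of contact, cannot be recovered when the data are analysed. That risk applies to suprapubic discomfort generally and to ototoxicity in women reached only by telephone.

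Hospital admission has a different problem. It is worded in several ways, so the event reviewed every 6 months need not be the event compared at the end.

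**Working it through.** The plan states no figure on this point, so the main check sets its sections side by side.

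| Event | Adverse-event paragraph (Data Collection) | Chart-extraction item (Data Collection) | Named at 6-week visit | Named in telephone call | By-arm comparison |
|---|---|---|---|---|---|
| Suprapubic discomfort | Yes, focus | None | No | No | No |
| Antibiotic-resistant UTI | Yes, focus | Culture result; resistance not defined | Culture if UTI symptoms | UTI treatment and symptoms only | No |
| Ototoxicity (four symptoms) | Yes, FDA request | Yes | Yes | No | No |
| Hospital admission | Yes; also as unanticipated admission | Readmission | Open question | Open question | Only with organ dysfunction |
| Death | Yes | None | – | – | Yes |
| Diarrhea | No | None | Open question | Open question | Yes |
| Yeast infection | No | None | Open question | Open question | Yes |

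**Step 1, analysis list.** The adverse-event paragraph names five events. Three are absent from the by-arm comparison, one is narrowed and one matches: 3 + 1 + 1 = 5. Diarrhea and yeast infection are compared but are not named as targets.

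**Step 2, is the compared list open or closed?** The phrase about each type of event could be read as covering every type. However, the parenthesis that follows carries no words such as *for example* or *including*. The natural reading is that the four items are the list.

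**Step 3, admission wording.** There are four versions: readmission (extraction), admission (recording), unanticipated admission (6-monthly review) and admission with organ dysfunction (comparison).

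**Step 4, precision of descriptive by-arm estimates.** The plan gives 166 women per arm needed and 200 recruited. The method is an exact unconditional 95% interval for the risk difference, obtained by inverting the score test.

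- With 0 events in both arms, the score statistic at a true difference d satisfies Z² = n·d/(1 − d). Setting Z = 1.96 gives the large-sample limit d = 3.84/(n + 3.84).
- At n = 166 this is 3.84/169.84 = 2.3 points. The exact calculation is slightly wider: p = 0.064 at 2.36 points and 0.045 at 2.40 points, so the limits are about ±2.4 points.
- At n = 200 the large-sample limit is 3.84/203.84 = 1.9 points, and the exact limits are about ±2.0 points.
- With assumed counts of 8 and 3 among 166 each, the difference is 5/166 = 3.0 points, with exact limits of about −1.0 to +7.8.

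**Step 5, size of the telephone gap.** The share of ototoxicity reports lost is the share reached only by telephone × (1 − share captured by an open question). Neither input is in the documents. Assuming 10% by telephone and 50% captured, the loss is 0.10 × 0.5 = 5%. With 5% to 20% by telephone it is 2.5% to 10%.

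**The case against.** The strongest reply is that the plan already commits to these data. The adverse-event paragraph says suprapubic discomfort data will be gathered. The 6-monthly review presumes that adverse events sit in the database, and the open 6-week question can bring the symptom out. The chart-extraction items are a general list, alongside length of stay and catheter days, and not a safety list. Death is missing from it too, yet the plan says deaths will be recorded. All of this stands. A reader might infer from the missing field that suprapubic discomfort will not be collected. The documents do not support that. They show only that the method of collection is not specified.

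A reader might also infer that the FDA's request is not met. What is visible is a request for monitoring and a recommendation for 6-week questions, and the plan provides questions, an extraction item and periodic review. Nothing visible says that the FDA asked for a between-arm comparison, and the correspondence is an attachment not available here.

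Finally, by-arm reporting may be intended through the words about each type of event or through the full listing. If so, the remedy is a change of wording. As printed, neither secures it: the parenthesis restricts the first, and the second is not stated to be by arm and gives no estimate of a difference.

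**Conclusion.** The point holds as a mismatch between the stated safety targets and the planned by-arm comparison, together with two gaps in how symptoms are asked about. Three of the five events in the adverse-event paragraph have no by-arm comparison as printed, and admission is narrowed. This rests on the text alone, and on reading the parenthesis as a complete list.

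It should be corrected, but its reach is limited. The primary analysis does not change. For ototoxicity and resistance, the visit data and cultures would still allow a table. The telephone gap is small, about 5% of reports (2.5% to 10%) under the assumed inputs. For suprapubic discomfort, the amount of under-reporting cannot be derived from the documents.

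It is tempting to express the harm as lost power. That would need event rates and capture rates that the plan does not give, for a test that should not be run on these rows. The interval widths are the relevant measure: about ±2.4 points at 166 per arm if no events occur, and wider when they do.

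**What to change.** 1. In Data Analysis/Interpretation, keep the existing events and add: any ototoxicity symptom, with the four symptoms tabulated; antibiotic-resistant UTI, with all women randomised to or treated in the arm as denominator (state which) and the culture result that defines resistance; and suprapubic discomfort.
2. Reconcile the admission wordings into one definition, chosen by the sponsor, that counts admissions after discharge from the index stay. Use it in extraction, review and comparison.
3. Ask about suprapubic discomfort by name at the existing 6-week contact, in the same words in both arms, and record whether it occurred in the early postoperative period. Because the catheter is clamped for only about 1 hour, recall at 6 weeks may miss discomfort from the instillation, so also note any report in the existing recovery-unit and chart records.
4. Ask the suprapubic and ototoxicity questions in the same words by telephone.
5. Provide a data field for every compared event, including diarrhea, yeast infection and death.
6. Report the added events by arm as counts and risk differences with exact 95% intervals, and state that they are descriptive.

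The cost is one added question, a few more items in an existing call, some data fields and several table rows. A limit remains: recall at 6 weeks cannot fully separate instillation discomfort from surgical pain. The interpretable result is therefore the difference between arms, not the rate in either arm.

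### The trial is sized on a one-tailed test but analysed with a chi-squared test at 0.05, which rejects in both directions; power is then about 70%, not 80%.

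*Combined protocol and SAP*

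**What the plan says.** Everything relevant is in section 9, under Data Analysis/Interpretation.

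- **Analysis.** "The primary outcome of the study, proportion of patients who are clinically treated for UTI, will be analyzed with a chi-squared test". Adverse-event proportions are compared by the same kind of test. One sentence then sets the threshold for all of these: "Statistical significance will be defined as" alpha below 0.05. Neither sentence gives a direction.
- **Sizing.** "To detect a meaningful reduction in UTI from 17% in controls to 8% in intervention group", the plan takes alpha 0.05, "one-tailed) with 80% power", and concludes that "166 subjects will be needed per arm".
- **Recruitment.** "Accounting for 20% dropout or loss to follow-up, we will recruit 200 subjects per arm".

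The term one-tailed occurs only in the sizing sentence, and no reason is given for it. No other part of the document states the sidedness of the primary test.

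**The concern.** The sizing calculation and the analysis text imply different rejection rules. The sizing rejects when z exceeds 1.645 in the favourable direction. The Pearson chi-squared statistic for two proportions is the square of z, so comparing its p-value with 0.05 rejects when the statistic exceeds 3.84, that is, when z lies beyond 1.96 in either direction.

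Two things are at stake. First, a trial analysed as written does not have the power it claims. Second, results with z between 1.645 and 1.96 are positive under the sizing rule and negative under the analysis rule. If the choice between them is left until the data are in, it is open to the criticism that the result drove it.

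**Working it through.** **Inputs, all from Data Analysis/Interpretation.** Control rate p1 = 0.17; intervention rate p2 = 0.08; difference 0.09; alpha 0.05; power 80% (z = 0.8416); equal arms; 166 evaluable and 200 recruited per arm; 20% loss.

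**Formula.** Pooled-variance formula for two proportions, without continuity correction:

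n per arm = (z_alpha × A + z_beta × B)² / (p1 − p2)²

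- Mean rate = (0.17 + 0.08)/2 = 0.125, so A = √(2 × 0.125 × 0.875) = √0.21875 = 0.4677.
- B = √(0.17 × 0.83 + 0.08 × 0.92) = √0.2147 = 0.4634.

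**Step 1: reproduce the plan's figure (one-tailed, z_alpha = 1.645).**

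n = (1.645 × 0.4677 + 0.8416 × 0.4634)² / 0.0081 = (0.7693 + 0.3900)² / 0.0081 = 165.9, rounded up to **166**. This matches.

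**Step 2: the same inputs, two-sided (z_alpha = 1.960).**

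n = (0.9167 + 0.3900)² / 0.0081 = 210.8, rounded up to **211**.

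Other common two-sided formulas give 209 (unpooled variance), 206 (arcsine) and 233 (continuity-corrected). None gives 166, so the plan's figure is a one-tailed one.

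**Step 3: power of each rule at the sample sizes in the plan.**

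Power = Φ[(0.09 × √n − z_alpha × A) / B]

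For example, at n = 166 two-sided: (0.09 × 12.884 − 0.9167) / 0.4634 = 0.524, and Φ(0.524) = 0.700.

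| Evaluable per arm | One-sided 0.05 | Two-sided 0.05 |
|---|---|---|
| 160 (200 less 20%) | 78.7% | 68.4% |
| 166 (plan's target) | 80.0% | 70.0% |
| 200 (no loss) | 86.1% | 77.9% |

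Exact binomial enumeration of the uncorrected chi-squared test at 166 per arm gives 81.2% one-sided and 71.1% two-sided. With the Yates correction the two-sided figure is 65.1%.

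**Step 4: results on which the two rules disagree (166 per arm, uncorrected).**

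| Control | Gentamicin | z | One-tailed p | Chi-squared p |
|---|---|---|---|---|
| 28/166 (16.9%) | 16/166 (9.6%) | 1.94 | 0.026 | 0.052 |
| 28/166 (16.9%) | 17/166 (10.2%) | 1.76 | 0.039 | 0.078 |

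Under the design rates, the exact probability of landing in this zone of disagreement is about 10% (81.2% − 71.1%).

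**The case against.** The best defence is that the plan never calls the primary test two-sided. Its only statement on sidedness is one-tailed, attached to the primary comparison and with the direction given as a reduction. The sponsor may intend the signed root of the chi-squared statistic, or a halved p-value. On that reading 166 per arm does give 80% power, and the fault is an omission in the analysis paragraph. It is also fair to say that the arithmetic behind 166 is right and that the one-tailed choice is disclosed next to the alpha.

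These points stand as far as they go. Two-sided is an inference from the named test, although a sound one: an analyst who runs that test and compares its p-value with 0.05 gets the two-sided result. The one-sided reading needs a step that the analysis text does not contain. The text has to change under either reading.

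Two smaller points also stand. That the 0.05 threshold covers adverse events as well, where either direction matters, makes the two-directional reading more natural but does not prove it for the primary outcome. And part of the shortfall at 160 per arm has another cause. The 200 corresponds to 166 × 1.2 = 199.2, whereas allowing for 20% loss requires 166/0.8 = 207.5, or 208. Power at 160 is below 80% even one-sided (78.7%), so the part due to sidedness there is the fall from 78.7% to 68.4%.

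**Conclusion.** The concern holds. The sizing and the stated analysis use different critical values. With the chi-squared test run as written at 0.05, power for 17% against 8% is about 70% at 166 evaluable per arm, so the chance of missing the targeted effect is about 30% rather than 20%. Recruiting 200 does not close the gap: power is 68% with the planned loss and 78% with none. These figures assume the plan's two rates, equal arms and no continuity correction; with the Yates correction, power would be lower. If a one-sided test at 0.05 is what the sponsor means, 80% at 166 is right, but the analysis text does not say so. This should be settled before outcome data are analysed, because it sets the decision rule for the primary outcome.

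**What to change.** State the sidedness of the primary test in the analysis paragraph and use the same critical value in the sample size paragraph.

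- **If two-sided**, the natural reading of the named test: write that the primary chi-squared test is two-sided at 0.05, and restate power for 17% against 8% as about 70% at 166 evaluable per arm, 68% at 160 and 78% at 200.
- **If one-sided is truly intended**: write in the analysis paragraph that the primary test is one-sided at 0.05 in the direction of a lower UTI rate with gentamicin, and say how the one-sided p-value is obtained. The 80% at 166 then stands.

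Either is a change of wording and requires no extra patients. The cost of the first is a less favourable stated power. Only if the sponsor wants to keep 80% power two-sided would the trial grow, to 211 evaluable per arm, or 211/0.8 = 263.75, that is 264 recruited per arm at 20% loss.
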